5.3 Flowchart of the study cohort assembly

	Optum	Truven	Medicare

	Less Excluded Patients	Remaining Patients	Less Excluded Patients	Remaining Patients	Less Excluded Patients	Remaining Patients
All patients in the database		74,864,884		191,990,035		23,466,175
Patients who used exposure or a reference between 20 January 2010 to Dec 2017 (for Marketscan)/March 2019 (for Optum) and 01 January 2012-December 2017 for Medicare	-73,333,681	1,531,203	-189,850,391	2,139,644	-20,002,243	3,463,932
Patients who have continuous 6 months registration in the database	-198,718	1,332,485	-233,411	1,906,233	-926,605	2,537,327
Patients without prior use of reference	-837,680	494,805	-1,282,498	623,735	-1,516,234	1,021,093
Patients without prior use of exposure	-58,834	435,971	-71,555	552,180	-57,547	963,546
Excluded because patient qualified in >1 exposure category	-193	435,778	-301	551,879	-111	963,435
Patients who did not have missing age information	-13	435,765	0	551,879	0	963,435
Patients who did not have missing gender information	-26	435,739	0	551,879	0	963,435
Excluded based on Inclusion 1- DM Type 2	-20,512	415,227	-49,327	502,552	-8,942	954,493
Excluded based on Inclusion 2- Age >=40	-8,101	407,126	-17,260	485,292	0	954,493
Excluded based on Inclusion 4- High risk for a CV event defined as having either established CV disease and/or multiple risk factors	-34,138	372,988	-73,801	411,491	-3,577	950,916
Excluded based on Exclusion1- CCI >=10	-3,466	369,522	-1,659	409,832	-17,277	933,639
Excluded based on Exclusion 2- treatment with an incretin-based therapy such as DPP-4 inhibitors and/or GLP-1 mimetics	-13,198	356,324	-18,748	391,084	-33,418	900,221
Excluded based on Exclusion 3- Acute vascular (cardiac or stroke) event <2 months [i.e. ACS/unstable angina OR Any stroke (inpatient, any)]	-766	355,558	-1,546	389,538	-1,979	898,242
Excluded based on Exclusion 4- chronic dialysis or renal transplant	-592	354,966	-434	389,104	-2,718	895,524
Excluded based on Exclusion 5- Pregnancy	-7	354,959	-11	389,093	-9	895,515
Excluded based on Exclusion 6- HIV/AIDS (dx and meds) with ICD10 CODES	-129	354,830	-104	388,989	-206	895,309
Excluded based on Exclusion 7- Lupus	-174	354,656	-122	388,867	-517	894,792
Excluded based on Exclusion 8- long-term (>30 consecutive days) oral corticosteroids use	-2,286	352,370	-2,495	386,372	-7,501	887,291
Excluded based on Exclusion 9- Morbid Obesity	-3,600	348,770	-2,126	384,246	-6,087	881,204

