	Composite of cardiovascular death, nonfatal myocardial infarction, or nonfatal ischemic stroke HR = 1.00 (95% CI 0.89-1.12)	
Measured 1 days after drug initiation in diagnosis position specified below and inpatient care setting:
 
Inpatient mortality/MI/Stroke --
 
For MI Any diagnosis position in inpatient care setting ICD-9 Dx 410.X (acute myocardial infarction) excluding 410.x2 (subsequent episode of care), as the principal (primary) or the next (secondary) diagnosis
 
For stroke Primary diagnosis position in inpatient care setting ICD-9 discharge diagnosis: 430.xx Subarachnoid hemorrhage (SAH) 431.xx Intracerebral hemorrhage (ICH) 433.x1 Occlusion and stenosis of precerebral arteries with cerebral infarction 434.xx (excluding 434.x0) Occlusion and stenosis of cerebral arteries with cerebral infarction 436.x Acute, but ill-defined cerebrovascular events
 
Mortality- See Mortality Sheet.
	
For MI:
 
►PPV 94% in Medicare claims data [Kiyota Y, Schneeweiss S, Glynn RJ, Cannuscio CC, Avorn J, Solomon DH. Accuracy of Medicare claims-based diagnosis of acute myocardial infarction: estimating positive predictive value on the basis of review of hospital records. American heart journal 2004;148:99-104.]
 
►PPV 88.4% in commercially-insured population [Wahl PM, Rodgers K, Schneeweiss S, et al. Validation of claims-based diagnostic and procedure codes for cardiovascular and gastrointestinal serious adverse events in a commercially-insured population. Pharmacoepidemiology and Drug Safety 2010;19:596-603.]
 
For stroke:
 
PPV of 85% or higher for ischemic stroke PPV ranging from 80% to 98% for hemorrhagic stroke
 
 
 
	Can't be measured in claims but not important for the analysis
	INCLUSION CRITERIA			

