1	Diagnosed with T2DM based on the current American Diabetes Association guidelines	Patients with a diagnosis of T2DM (ICD-9 Dx code of 250.x0 or 250.x2) in the 180 days prior to drug initiation in any diagnosis position and inpatient or outpatient care setting .	Patorno, Elisabetta et al. "Cardiovascular outcomes associated with canagliflozin versus other non-gliflozin antidiabetic drugs: population based cohort study." BMJ 2018;360:k119 http://dx.doi.org/10.1136/bmj.k119	
2	Age ≥40 years	Age ≥40 years at drug initiation	Patorno, Elisabetta et al. "Empagliflozin and the Risk of Heart Failure Hospitalization in Routine Clinical Care: A First Analysis from the Empagliflozin Comparative Effectiveness and Safety (EMPRISE) Study." Circulation. 2019 Apr 8. doi: 10.1161/CIRCULATIONAHA.118.039177	
3	Glycated hemoglobin level of ≥6.5% (based on the last measured and documented laboratory measurement in the previous 6 months)	N/A		
4	High risk for a CV event defined as having either established CV disease and/or	-		
	• History of established cardiovascular disease -Ischemic heart disease, and/or	Measured 180 days prior to drug initiation in any diagnosis position and inpatient or outpatient care setting - Ischemic heart disease 410.xx-414.xx	Patorno, Elisabetta et al. "Cardiovascular outcomes associated with canagliflozin versus other non-gliflozin antidiabetic drugs: population based cohort study." BMJ 2018;360:k119 http://dx.doi.org/10.1136/bmj.k119	
			Patorno, Elisabetta et al. "Empagliflozin and the Risk of Heart Failure Hospitalization in Routine Clinical Care: A First Analysis from the Empagliflozin Comparative Effectiveness and Safety (EMPRISE) Study." Circulation. 2019 Apr 8. doi: 10.1161/CIRCULATIONAHA.118.039177	

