3	Acute vascular (cardiac or stroke) event <2 months before randomization	Measured 60 days prior to drug initiation in any diagnosis/procedure position and inpatient care setting - ACS/unstable angina 411.xx Any stroke ICD-9 Dx: 430.xx, 431.xx, 433.xx, 434.xx, 436.xx	Patorno, Elisabetta et al. "Cardiovascular outcomes associated with canagliflozin versus other non-gliflozin antidiabetic drugs: population based cohort study." BMJ 2018;360:k119 http://dx.doi.org/10.1136/bmj.k119 Patorno, Elisabetta et al. "Empagliflozin and the Risk of Heart Failure Hospitalization in Routine Clinical Care: A First Analysis from the Empagliflozin Comparative Effectiveness and Safety (EMPRISE) Study." Circulation. 2019 Apr 8. doi: 10.1161/CIRCULATIONAHA.118.039177
4	Initiation of chronic dialysis and/or renal transplant and/or a serum creatinine >6.0 mg/dL	Measured 180 days prior to drug initiation in any diagnosis position and inpatient or outpatient care setting - Kidney transplant Codes include: -ICD9 dx codes: o V42.0x, Kidney transplant status o 996.81 Complications of transplanted kidney -ICD9 prox codes: o 55.6x, Transplant of kidney (Exclude 55.61) -CPT4 codes: o 50360, Renal allotransplantation, implantation, graft, w/o donor & recipient nephrectomy o 50365, Renal allotransplantation, implantation, graft, w/ donor & recipient nephrectomy Dialysis (Please see Dialysis sheet)	Patorno, Elisabetta et al. "Cardiovascular outcomes associated with canagliflozin versus other non-gliflozin antidiabetic drugs: population based cohort study." BMJ 2018;360:k119 http://dx.doi.org/10.1136/bmj.k119 Patorno, Elisabetta et al. "Empagliflozin and the Risk of Heart Failure Hospitalization in Routine Clinical Care: A First Analysis from the Empagliflozin Comparative Effectiveness and Safety (EMPRISE) Study." Circulation. 2019 Apr 8. doi: 10.1161/CIRCULATIONAHA.118.039177
5	Pregnant or breastfeeding	Measured 180 days prior to drug initiation in any diagnosis position and inpatient or outpatient care setting- Pregnancy : Please see Pregnancy sheet.	

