Appendix A

4a	
Measured 180 days prior to drug initiation in any diagnosis position and inpatient or outpatient care setting - Peripheral vascular disease ICD9 diagnosis: 440.20–440.24, 440.29–440.32, 440.3, 440.4, 443.9
 
–Peripheral vascular disease (eg, intermittent claudication), and/or
		
Patorno, Elisabetta et al. "Cardiovascular outcomes associated with canagliflozin versus other non-gliiflozin antidiabetic drugs: population based cohort study." BMJ 2018;360:k119 http://dx.doi.org/10.1136/bmj.k119
 
Patorno, Elisabetta et al. "Empagliflozin and the Risk of Heart Failure Hospitalization in Routine Clinical Care: A First Analysis from the Empagliflozin Comparative Effectiveness and Safety (EMPRISE) Study." Circulation. 2019 Apr 8. doi: 10.1161/CIRCULATIONAHA.118.039177

	
–Ischemic stroke
 
Measured 180 days prior to drug initiation in any diagnosis position and inpatient or outpatient care setting - Any stroke: ICD-9 Dx: 433.xx, 434.xx, 436.xx
		
4b	
• Multiple risk factors for vascular disease
 
–At least 55 years of age (men) or 60 years of age (women), AND at least one of the following additional risk factors
		
	
* Dyslipidemia (based on the last measured and documented laboratory measurement in the previous 6 months and defined as at least 1 of the following):
	
At least 55 years of age (men) or 60 years of age (women) at drug initiation, AND
 
Measured 180 days prior to drug initiation in any diagnosis position and inpatient or outpatient care setting - Hyperlipidemia 272.0x-272.4x
	
Patorno, Elisabetta et al. "Cardiovascular outcomes associated with canagliflozin versus other non-gliiflozin antidiabetic drugs: population based cohort study." BMJ 2018;360:k119 http://dx.doi.org/10.1136/bmj.k119
 
Patorno, Elisabetta et al. "Empagliflozin and the Risk of Heart Failure Hospitalization in Routine Clinical Care: A First Analysis from the Empagliflozin Comparative Effectiveness and Safety (EMPRISE) Study." Circulation. 2019 Apr 8. doi: 10.1161/CIRCULATIONAHA.118.039177

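### Exclusion 3 targets recent acute cardiac or stroke events, but its printed codes omit acute myocardial infarction (410.xx) and no other printed exclusion removes it

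*Protocol*

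**What the plan says.** Appendix A, Exclusion criterion 3, gives the trial's rule as "Acute vascular (cardiac or stroke) event <2 months before randomization". The routine-care column implements it over the 60 days before initiation, inpatient, any position, with "ACS/unstable angina 411.xx Any stroke ICD-9 Dx: 430.xx, 431.xx, 433.xx, 434.xx, 436.xx". The Combined protocol and SAP prints the same list.

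The flowchart in Section 5.3 labels the step "Acute vascular (cardiac or stroke) event <2 months [i.e. ACS/unstable angina OR Any stroke (inpatient, any" (closing brackets cut). It reports 766 (Optum), 1,546 (MarketScan/Truven) and 1,979 (Medicare) patients removed.

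Elsewhere Appendix A does code acute MI. The primary outcome uses "ICD-9 Dx 410.X (acute myocardial infarction) excluding 410.x2 (subsequent episode of care" (closing bracket cut), with supporting validation figures: "PPV 94% in Medicare claims data" and "PPV 88.4% in commercially-insured population". Inclusion criterion 4 counts "Ischemic heart disease 410.xx-414.xx" in the prior 180 days as established cardiovascular disease.

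Section 5.2.2 says the trial's criteria were followed as closely as possible. Section 5.1 starts follow-up the day after initiation.

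**The concern.** Acute MI is a central example of an acute cardiac event and a component of the primary outcome. An exclusion written to remove recent acute cardiac events, but coded without MI, admits patients it is meant to keep out. The study exists to reproduce one trial's estimate, so matching that trial's population matters in its own right.

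There is a second, smaller risk. Follow-up opens the day after initiation and the outcome counts inpatient 410.X codes other than 410.x2. A readmission or transfer belonging to a pre-entry MI could therefore be recorded as an outcome event. The documents give no rate for this.

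**Working it through.** **1. Code lists side by side (Appendix A)**

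| Place | Codes | 410.xx? |
|---|---|---|
| Inclusion 4, ischaemic heart disease | 410.xx-414.xx | yes, qualifies for entry |
| Primary outcome, MI | 410.X without 410.x2 | yes |
| Exclusion 3 | 411.xx, 430, 431, 433, 434, 436 | no |
| Remaining exclusions (comorbidity score, incretins, dialysis/transplant, pregnancy, HIV, lupus, oral steroids, morbid obesity, non-compliance) | own lists | no |

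That 410.xx qualifies under Inclusion 4 is not itself the fault. 411.xx qualifies there too, as do the stroke codes ("Any stroke: ICD-9 Dx: 433.xx, 434.xx, 436.xx" in the Combined protocol and SAP), and Exclusion 3 then overrides them when the event is recent. For MI, nothing overrides.

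**2. Could the ACS label include MI?** Appendix A prints that label as 411.xx, and Table 1 has separate rows for acute MI and ACS/unstable angina. In the unmatched reference arm the acute MI count is the larger in every database: Optum 5,645 v 5,370, MarketScan 5,977 v 5,093, Medicare 13,796 v 12,672. If the two rows share a window and setting (not stated), acute MI cannot be a subset of the ACS row.

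**3. The plan's own figures.** The Exclusion 3 flowchart row is exact: 356,324 - 766 = 355,558; 391,084 - 1,546 = 389,538; 900,221 - 1,979 = 898,242. In total 4,291 of 1,647,629 were removed (0.26%).

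**4. Possible size.** Matched acute MI records (Table 1, reference + exposed):
- Optum 233 + 244 = 477 of 41,544 (1.1%)
- MarketScan 282 + 300 = 582 of 58,300 (1.0%)
- Medicare 483 + 471 = 954 of 82,282 (1.2%)
- Total 2,013 of 182,126 (1.1%)

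The row's codes, setting and window are not given, so 2,013 is not a bound. Assuming the 180-day default of Section 6.2 and an even spread, 60/180 of 2,013 = 671 (0.37%).

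A loose outer limit that avoids this row: an inpatient MI in the prior 60 days requires a hospital stay in the prior 180 days. Matched patients with any hospitalisation number 7,619 + 7,419 = 15,038 (8.3%). This reads that row as covering 180 days, as its companion rows (prior 30 days, prior 31-180 days) suggest.

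**5. Power cost of removal.** With d events and 1:1 allocation, power = Φ(|ln HR|·√d/2 - 1.96), using HR 1.3 for non-inferiority and 0.83 for superiority. This reproduces Section 10: Optum d = 568.3 gives 0.8785 and 0.6030; MarketScan d = 945.0 gives 0.9809 and 0.8170; Medicare d = 3,158.0 gives superiority 0.9995.

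Illustrative scenarios, because they rest on the acute MI row:
- A: drop each exposed patient with an acute MI record and the matched place, at average risk. Optum: d = 568.3 - 2·244·0.01368 = 561.6.
- B: drop all matched acute MI patients at an assumed 5 times average risk. Optum: d = 568.3 - 5·477·0.01368 = 535.7.
- C: as B, and also drop one partner each at average risk. Optum: d = 568.3 - 6·477·0.01368 = 529.2.

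| Non-inferiority / superiority | Section 10 | A | B | C |
|---|---|---|---|---|
| Optum | 87.8% / 60.3% | 87.5% / 59.8% | 85.9% / 57.8% | 85.5% / 57.3% |
| MarketScan | 98.1% / 81.7% | 98.0% / 81.3% | 97.6% / 79.7% | 97.4% / 79.3% |

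Medicare superiority goes from 99.95% to 99.94%, 99.91% and 99.90%. Pooled superiority stays above 99.9% under B, both on the protocol's 4,145 events (3,916 left) and on the 4,671 obtained by summing the databases (4,408 left).

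**The case against.** The strongest reply is that nothing here is shown to move the result. Matched acute MI is balanced (998 v 1,015, standardised difference 0.00), carry-over equal in both arms leaves a hazard ratio of 1.00 where it is, and the plan openly leaves wider gaps, such as the HbA1c threshold, which is marked not applicable. That stands as to the hazard ratio. It does not excuse the omission, because those criteria are declared unmeasured, whereas MI can be coded and is coded in the same appendix.

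Second, the executed definition is partly outside the documents: Appendix A refers to an external folder for ICD-10 lists and supplementary detail, and the row's colour grade is unreadable, so it may have been marked as an imperfect mapping. This limits what can be said about the cohort actually built. However, the appendix says the ICD-10 codes were mapped from ICD-9, so a gap in one list would be expected in the other.

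Third, leaving 410.x2 out of the outcome is a guard against counting continuing care of an earlier MI. It is a partial guard, and how far it falls short is unknown.

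Fourth, the cited predictive values belong to the outcome algorithm, not to an any-position 410.xx exclusion. They show that MI is identifiable in these data; they do not validate the proposed list.

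Finally, Table 1 does not prove that any MI within 60 days remained. The records could fall on days 61-180 or come from outpatient claims, and a patient with an inpatient 411.xx code as well would already be removed. ACS/unstable angina, which is on the exclusion list, also remains at 1.4-1.5%.

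**Conclusion.** The concern holds. On the printed record, the code list for Exclusion 3 does not implement its own criterion, and no other printed exclusion closes the gap. It should be fixed, though it does not invalidate the study.

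Confidence is high for the printed omission. It does not extend to how many recent-MI patients are in the cohort: that count is not in the documents, and 671 (0.37% of matched patients) rests on an assumed 180-day window and an even spread. The established consequence is a cohort less faithful to the trial than the available codes allow. Carry-over into the outcome is possible and unquantified. Confounding of the primary hazard ratio is not claimed.

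**What to change.** First establish whether 410.xx was in the executed list, and report the number of patients with an inpatient 410.xx code in the 60 days before initiation, by arm and database.

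- **If it was not in the list:** add inpatient 410.xx and its ICD-10 equivalents, any position, 60 days, to Exclusion 3, stating how 410.x2 is handled. Re-run the flowchart, match, balance and power tables, and take them through the Section 9-10 review again before the Section 13 analysis, whose date field is still blank.
- **If it was in the list:** print it in Appendix A and correct the flowchart label.
- **If the omission is deliberate:** state the reason and report the primary hazard ratio with and without these patients.

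The programming cost is one code set in an existing query plus the re-runs. The power cost is small in the scenarios above. The main burden is repeating a review recorded as completed on 12/9/19 (investigator) and 12/20/19 (FDA), which also involves the advisory board.

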Appendix A

7	Patients being treated for severe autoimmune diseases such as lupus	Measured 180 days prior to drug initiation in any diagnosis/procedure position and inpatient care setting Lupus 373.34 - (ICD9) DISCOID LUPUS ERYTHEMATOSUS OF EYELID 710.0 - (ICD9) SYSTEMIC LUPUS ERYTHEMATOSUS	
8	Any patient currently receiving long-term (>30 consecutive days) treatment with an oral steroid	Measured 180 days prior to drug initiation as a dispensing of one of the following drugs - Oral corticosteroids: Cortisone, hydrocortisone, prednisone, prednisolone, methylprednisolone, triamcinolone, dexamethasone, betamethasone.	Patorno, Elisabetta et al. "Cardiovascular outcomes associated with canagliflozin versus other non-gliflozin antidiabetic drugs: population based cohort study." BMJ 2018;360:k119 http://dx.doi.org/10.1136/bmj.k119 Patorno, Elisabetta et al. "Empagliflozin and the Risk of Heart Failure Hospitalization in Routine Clinical Care: A First Analysis from the Empagliflozin Comparative Effectiveness and Safety (EMPRISE) Study." Circulation. 2019 Apr 8. doi: 10.1161/CIRCULATIONAHA.118.039177
9	Patients with		
9a	• Body mass index >50 kg/m ²	Measured 180 days prior to drug initiation in any diagnosis/procedure position and inpatient care setting- Morbid Obesity 278.01 - (ICD9) MORBID OBESITY	
9b	• Last measured HbA1c ≥12%	N/A	
9c	• Sustained BP >180/100 mm Hg	N/A	
9d	• LDL-C >250 mg/dL (>6.48 mmol/L) (based on the last measured and documented laboratory measurement in the previous 6 months) regardless of lipid-lowering therapy	N/A	
9e	• Triglycerides >1,000 mg/dL (N11.3 mmol/L) (based on the last measured and documented laboratory measurement in the previous 6 months)	N/A	
9f	• HDL-C <25 mg/dL (<0.64 mmol/L) (based on the last measured and documented laboratory measurement in the previous 6 months)	N/A	
9g	• Known liver function tests >3 times upper limit of normal (ULN) (based on the last measured and documented laboratory measurement in the previous 6 months)	N/A	
10	Involvement in the planning and/or conduct of the study (applies to both AstraZeneca and Bristol-Myers Squibb or representative staff and/or staff at the study site)	N/A	
11	Previous randomization in the present study	N/A	
12	Participation in another clinical study with an investigational product and/or intervention within 30 days before visit 1	N/A	
13	Individuals at risk for poor protocol or medication compliance	Measured 180 days prior to drug initiation in any diagnosis/procedure position and inpatient care setting- Non-compliance V15.81 - (ICD9) PERSONAL HISTORY OF NONCOMPLIANCE WITH MEDICAL TREATMENT PRESENTING HAZARDS TO HEALTH V45.12 - (ICD9) NONCOMPLIANCE WITH RENAL DIALYSIS	

Appendix A

Trial ID	Neg5
Trial Name (with web links)	SAVOR- TIMI 53
Trial Name (with pdf links)	SAVOR- TIMI 53
NCT	NCT01107886
Trial category	Negative trial
Therapeutic Area	Endocrinology
RCT Category	2b- Failed S with NI- No label change
Brand Name	Onglyza
Generic Name	saxagliptin
Sponsor	AstraZeneca Bristol-Myers Squibb
Year	2013
Measurable endpoint	Primary composite endpoint of Cardiovascular Death (CV Death), Non-fatal Myocardial Infarction (MI), or Non-fatal Ischaemic Stroke
Exposure	Saxagliptin
Comparator	Placebo
Population	patients with type 2 diabetes who had a history of, or were at risk for, cardiovascular events. The concomitant Anti-hyperglycemic and Cardiovascular Medications- 75% aspirin, 78% statins, 53% ACE, 61% beta-blockers
Trial finding	HR = 1.00 (95% CI 0.89-1.12)
Notes	
No. of Patients	18,206
Non-inferiority margin	HR = 1.3
Assay Sens. Endpoint	From trial- Hospitalization for heart failure. Alternative suggestion- all-cause mortality/MACE/hypoglycemia
Assay Sens. Finding	3.5% vs. 2.8%; hazard ratio, 1.27; 95% CI, 1.07 to 1.51; P=0.007
Comments/Notes	It is hard to replicate, so alternative option would be to replicate "all-cause mortality" / MACE/hypoglycemia as shown in this Taiwan study comparing DPP4i to sulfonylureas - http://annals.org/aim/article-abstract/2456123/effects-clinical-outcomes-adding-dipeptidyl-peptidase-4-inhibitors-versus-sulfonylureas
Power	0.85 power to identify a 17% relative reduction of the primary end point with saxagliptin versus placebo and 98% power to test for noninferiority of saxagliptin versus placebo (reject the upper limit of 95% CI for a hazard ratio <1.3 at a 1-sided α of .025)
Blinding	Double-blinded
Statistical Method	Superiority and non-inferiority
Approval indication	

Appendix A

Mortality- Dependent on data source.

1. All-cause mortality / inpatient mortality

Identified using the vital status file-

Medicare

Identified using the discharge status codes-

Optum-

- 20 = EXPIRED
- 21 = EXPIRED TO BE DEFINED AT STATE LEVEL
- 22 = EXPIRED TO BE DEFINED AT STATE LEVEL
- 23 = EXPIRED TO BE DEFINED AT STATE LEVEL
- 24 = EXPIRED TO BE DEFINED AT STATE LEVEL
- 25 = EXPIRED TO BE DEFINED AT STATE LEVEL
- 26 = EXPIRED TO BE DEFINED AT STATE LEVEL
- 27 = EXPIRED TO BE DEFINED AT STATE LEVEL
- 28 = EXPIRED TO BE DEFINED AT STATE LEVEL
- 29 = EXPIRED TO BE DEFINED AT STATE LEVEL
- 40 = EXPIRED AT HOME (HOSPICE)
- 41 = EXPIRED IN A MEDICAL FACILITY (HOSPICE)
- 42 = EXPIRED - PLACE UNKNOWN (HOSPICE)

Truven-

- 20 - Died
- 22 - Died
- 23 - Died
- 24 - Died
- 25 - Died
- 26 - Died
- 27 - Died
- 28 - Died
- 29 - Died
- 40 - Other died status or Expired at home (Hospice claims only) (depends on year)
- 41 - Other died status or Expired in medical facility (Hospice claims only) (depends on year)

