6.3.1 Outcome variables

Effectiveness outcomes of interest (definitions provided in **Appendix A**):

- **Primary outcome:** 3-point major adverse cardiovascular events (MACE), i.e., non-fatal myocardial infarction, non-fatal stroke, or CV mortality
- Secondary outcomes: Individual MACE components:
 - Hospital admission for MI (for purposes of this individual component, fatal MI is included)
 - Hospital admission for stroke (for purposes of this individual component, fatal stroke is included)
 - All-cause mortality/CV mortality:
 - All-cause inpatient mortality identified using discharge status codes will be used as a proxy for "CV mortality" in commercial databases
 - Information on CV mortality through data linkage with the National Death Index (NDI) will only become available at a later date for Medicare and will be used in secondary analyses.

Control outcomes of interest (control outcomes only serve to assess aspects of study validity but are not further interpreted):

1. Severe hypoglycemia (we expect to see protective effect; American Diabetes Association, 2018)

Control outcome definitions

Outcome	Hospital Discharge Code(s)	Comments
Severe hypoglycemia	Severe hypoglycemia Any-position ED or primary inpatient ICD-9 diagnosis: 251.0, 251.1x, 251.2x, or 250.8x. Outcomes identified by 250.8x are not included if they co-occur with one of the following diagnoses: 259.8, 272.7, 681.xx, 682.xx, 686.9, 707.1x, 707.2x, 707.8, 707.9, 709.3, 730.0x, 730.1x, 730.2x, 731.8	Note- The corresponding ICD-10 codes will be used also

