Appendix A

- 42 - Other died status or Expired - place unknown (Hospice claims only) (depends on year)
- 21 - Died or Disch./Transf. to court/law enforcement (depends on year)

2. CV mortality

Information on CV mortality through data linkage with the National Death Index (NDI) will be available for Medicare and Optum Clininformatics at a later date. We will conduct secondary analyses using CV mortality at that time.

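### The primary composite's death component is labelled inpatient mortality, but its code sheet uses vital-status deaths in Medicare and admits home-hospice codes and a Truven code that in some years is a live discharge

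*Protocol*

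**What the plan says.** The death component is described in three places. The wording is the same in the Protocol and in the Combined protocol and SAP.

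- **Section 6.3.1** names the primary outcome as "non-fatal myocardial infarction, non-fatal stroke, or CV mortality". It then states that "All-cause inpatient mortality identified using discharge status codes will be used as a proxy for" CV mortality in the commercial databases. For Medicare it mentions only cause of death from the National Death Index (NDI), available later and for secondary analyses.
- **Appendix A, primary-outcome row**, sets the inpatient care setting, gives the composite as "Inpatient mortality/MI/Stroke" without distinguishing databases, and adds "Mortality- See Mortality Sheet".
- **Appendix A, Mortality sheet**, opens with "Mortality- Dependent on data source". Under a heading that covers both all-cause and inpatient mortality, Medicare deaths are "Identified using the vital status file". Optum and Truven deaths come from discharge status codes 20 to 29 and 40 to 42. The Optum list includes "40 = EXPIRED AT HOME (HOSPICE" and, as code 42, a hospice death at an unknown place. The Truven list includes "21 - Died or Disch./Transf. to court/law enforcement (depends on year". No year rule and no restriction on claim type is given.

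**The concern.** The primary-outcome row and the sheet it points to do not describe the same event. A death at home is not an inpatient death, a vital status file is not an inpatient source, and a patient discharged to law enforcement is alive. Two programmers working from these pages could build different primary endpoints and both claim to have followed the plan.

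The primary hazard ratio (HR) will be set against a trial estimate of 1.00 for CV death, MI or ischemic stroke, and against a margin of 1.3. If the death component differs between databases and from its label, a difference between the Medicare HR and the commercial HRs could reflect either population or definition. The expected risks already show this: 38.38 per 1,000 in Medicare against 13.68 and 16.21 in Optum and MarketScan. Medicare patients are older, but how much of the gap comes from a broader death definition cannot be told.

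**Working it through.** **1. The texts side by side**

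| Source | Section 6.3.1 | Appendix A outcome row | Mortality sheet |
|---|---|---|---|
| Optum | all-cause inpatient death, discharge status | inpatient mortality | codes 20–29, 40–42; 40 and 42 are hospice deaths at home or at an unknown place |
| Truven/MarketScan | same | same | same codes; 21 and 40–42 change meaning by year |
| Medicare | no proxy stated for the primary analysis | inpatient mortality | vital status file, no inpatient limit stated |

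Optum and Truven share one code set, so there are two death definitions: discharge status and vital status.

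**2. The plan's event counts (Section 10)**

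Events = 2 × matched patients per arm × risk / 1,000.

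- Optum: 2 × 20,772 × 0.01368 = 568.3
- MarketScan: 2 × 29,150 × 0.01621 = 945.0
- Medicare: 2 × 41,141 × 0.03838 = 3,158.0
- Pooled, as the plan has it: 2 × 91,063 × 0.02276 = 4,145.2

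All four match the plan. The three databases sum to 4,671.3, not 4,145.2, because the pooled risk of 22.76 is the unweighted mean (13.68 + 16.21 + 38.38) / 3. Medicare's share is 3,158.0 / 4,671.3 = 67.6%.

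**3. How many events depend on the death definition**

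Section 9 reports 1,783 deaths in matched follow-up: 1,783 / 4,671 = 38% of the summed events, or 1,783 / 4,145 = 43% of the plan's pooled figure. This is an upper bound on the death-first share. The table comes from the run on the dummy enrollment-gap outcome, so some of these deaths would follow an MI or stroke already counted. It is not split by database, place or code.

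**4. Direction at the null**

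Deaths are 732 on saxagliptin and 1,051 on sulfonylureas, a risk ratio of 732 / 1,051 = 0.70. Follow-up is unequal. Weighting the Section 9 medians by matched N gives 138 days (saxagliptin) and 172 days (referent), a ratio of 1.24. The crude rate ratio is then about 0.70 × 1.24 = 0.87 (rough 95% CI 0.79 to 0.95). Equal rates would need follow-up to differ by 1,051 / 732 = 1.44-fold. This is only indicative: medians are a poor stand-in for person-time, and the arm-level rows for MarketScan and Medicare are identical while their overall rows differ, which suggests a copying error.

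**5. Effect on the composite**

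Let f be the share of composite events that are non-CV deaths and h their HR. Approximately, observed HR = (1 − f) × true CV-endpoint HR + f × h. The documents do not give f, so I assume 0.1 to 0.3.

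| f | true 1.00, h = 1 | true 1.00, h = 0.87 | true 1.30, h = 1 | true 1.30, h = 0.87 |
|---|---|---|---|---|
| 0.1 | 1.00 | 0.987 | 1.27 | 1.257 |
| 0.2 | 1.00 | 0.974 | 1.24 | 1.214 |
| 0.3 | 1.00 | 0.961 | 1.21 | 1.171 |

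At the null the result depends on h. At 1.30 the composite reads low for any h below 1.30.

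**The case against.** Several points on the other side stand.

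- **Disclosure.** The sheet says openly that mortality varies by data source, Section 6.3.1 confines the proxy to the commercial databases, and the lack of CV cause of death is acknowledged, with NDI analyses to follow. That does not reconcile the outcome row with the sheet or supply a Medicare rule.
- **Hospice codes may rarely apply.** Truven ties the place-of-death meanings of codes 40 to 42 to hospice claims. If only inpatient claims are searched, code 40 may seldom appear. The sheet also seems to serve the all-cause mortality secondary outcome. The plan does not say which claims are searched, and that is the gap.
- **A narrower definition is not plainly better.** The target is CV death wherever it occurs. Limiting Medicare to inpatient death loses out-of-hospital CV deaths, and deleting codes 40 to 42 would remove Truven records meaning some other died status.
- **Components are reported separately.** MI, stroke and mortality each get their own HR, so part of any dilution will be visible.

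Three stronger readings are tempting, and the documents do not support them. A reader might infer that the databases measure three different endpoints; there are two death definitions. A reader might infer that the HR must be pulled toward 1; that needs non-CV deaths unrelated to treatment, and the plan's deaths run 732 against 1,051. A reader might also assume 30–70% of the 1,783 deaths are non-CV with HR 1, obtain a false non-inferiority probability of about 15–59% at a true 1.30 (4,671 events), and blame the code sheet. The 30–70% has no source in the documents, and the inpatient proxy in Section 6.3.1 already admits non-CV deaths, so correcting the sheet alone would not remove that risk.

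**Conclusion.** The primary composite's death component is inconsistently specified. Section 6.3.1, the outcome row and the Mortality sheet cannot all be followed at once. The departure is largest in Medicare, which supplies about 68% of the summed expected events, and deaths could account for up to 38% of those events. Counting Truven code 21 without a year rule is an error by the sheet's own description, though confined to one database and certain years; no count is available.

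The direction of bias at a true HR of 1 is unknown. A true CV-endpoint HR near 1.3 would be understated unless non-CV deaths are raised to a similar degree, which makes non-inferiority easier to declare. The size rests on the assumed f and h. That Medicare counts deaths in any place is inferred from the use of a vital status file; the plan does not say so. Section 13 carries no conduct date, so by the document's own record the definition can still be settled before comparative results exist.

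**What to change.** 1. In the Mortality sheet, count Truven code 21 as death only in years when it means died.
2. Reconcile Section 6.3.1, the Appendix A outcome row and the Mortality sheet. For each database state the death source, claim type and eligible codes, whether hospice claims count toward the composite, and the Medicare rule for the primary analysis. Also align the NDI statements: Section 6.3.1 names Medicare only, Appendix A names Medicare and Optum.
3. Pre-specify two versions alongside the primary: a common-definition composite using inpatient death in all three databases, and one counting inpatient death only when the terminal stay's principal diagnosis is cardiovascular (or MI and stroke alone), until NDI cause of death is available.
4. Report database-specific HRs before the pooled estimate.

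The cost is a revised code list and a few extra outcome runs per database. The common-definition version will have fewer Medicare events; out-of-hospital deaths there remain in the all-cause mortality secondary outcome.
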